6.4 Per-protocol population

The per-protocol population is defined as all patients who are randomised to MA TKA or FA TKA and complete the study according to the protocol.

In the event that there are errors in the randomisation assignment, the analysis will be performed using the treatment that the patient actually received, not the assigned treatment. Patients will be considered protocol violators if they do not meet the eligibility criteria as outlined in the protocol. Other reasons to be considered a protocol violator include, but are not limited to, protocol violations, and any actions that compromise the effectiveness of the treatment, such as receiving a secondary treatment. Protocol violators will not be considered as part of the per-protocol population and will be listed separately with the reason for their exclusion from the per-protocol population.

6.5 Baseline Data

Baseline data will be recorded for each patient after completion of the consent form. This data will be recorded on Socrates, as detailed in the Data Management Plan (Section 9).

7.0 Patient and Public Involvement

This study will not actively include any patients or lay members of the public to assist in the study design, management, analysis of results or dissemination of findings. Patients will be provided with a lay summary of the research findings after completion of the study.

8.0 Funding and Supply of Equipment

Stryker Orthopaedics will be supplying the lachmeter and dynamometer for this study. St. John of God Healthcare currently fund a 1 FTE RP who will also assist in this project.

9.0 Data Handling and Management

9.1 Data Quality Assurance and Monitoring

The principle of Good Clinical Practice will be adhered to throughout with the research team responsible for its own regular internal audit for quality, recruitment goals and results targets. This will be in the form of monthly research meetings for those involved in the trial. The Investigator will designate one or more appropriately trained and qualified individuals to monitor the progress of the clinical study. As per section 2.1.1 of the NHMRC Code, all clinical trial research data will be retained for a minimum of 15 years from the date of publication or 5 years following the completion of the research.

9.2 Onsite Monitoring

On-site monitoring visits shall occur throughout the course of the clinical study by the Chief Investigator. The Chief Investigator shall permit and assist the IDSM (should they chose to monitor the study) to carry out verification of completed case report forms (CRFs) against data in the source

documents, which shall occur as per the departmental policy for undertaking such activities.

All personnel involved with the conduct of the study must undertake to maintain the confidentiality of patients in the study. The requirements of the current Good Clinical Practice guidelines will be adhered to for data processing.

10.0 Consent and Case Report Form Storage

All case report forms (CRFs) must be completed and signed by staff that are listed on the site staff delegation log and authorised by the CI/ PI to perform this duty. The CI/PI is responsible for the accuracy of all data reported in the CRF.

Data required according to this protocol are to be recorded on the CRFs as soon as possible. Patients will be identifiable with a unique study number. Only the research physiotherapist will have the key to identify individual patients. All CRFs must be legible and completed in black ink. Any necessary corrections are to be made by drawing a single line through the incorrect entry and writing in the revision, and must be initialed and dated by the investigator or his or her representative. Data are not to be obliterated by blacking out, using correction fluid or by erasing the original entry. Any documents related to the study must be archived directly at the study site. These documents include listings that identify study subjects, research group allocated to each study subject, consent forms, and all completed CRFs. All consent forms and CRFs will be stored by the CI/PI investigator in a locked filing cabinet in a dedicated locked research office. This office has key access with monitored security. Patient data will be logged electronically using each patient's unique identification number with Socrates computer software on an encrypted, password-protected research computer on the Perth Hip and knee clinic network. This computer is located within a dedicated lockable research office within Perth Hip and Knee Clinic Subiaco.

11.0 Assessment and Management of Risks

The trial will be conducted in full conformance with the principles of the Declaration of Helsinki and ICH Good Clinical Practice guidelines. All data will be stored securely and held in accordance with Data Protection Act 1998. The trial will be reported in line with the CONSORT statement.

Written informed consent will be obtained from all patients participating in the study. Patient safety is of paramount importance and all participants will be treated with respect and dignity throughout. Inclusion or exclusion from the study will not impact the quality of the care they receive. Participants will not receive any preferential treatment or payment for taking part in the study, and are free to leave the study at any point without any compromise to their further treatment.

There is no “safe” radiation dose but it is best clinical practice to limit radiation exposure as much as possible. Routine radiological follow-up of patients undergoing TKA at Perth Hip & knee Clinic includes

anteroposterior and lateral knee radiographs at discharge, and anteroposterior skyline and lateral radiographs at 1 year, and 2 years postoperatively. Additional standard long-leg radiographs are performed at 3 months following TKA. In this study, the same protocol will be adhered to with no additional radiation dose.

12.0 Recording and Reporting of adverse events

12.1 Definitions of Adverse Events

Term	Definition
Adverse Event (AE)	Any untoward medical occurrence in a patient or study participant, which does not necessarily have a causal relationship with the procedure involved.
Serious Adverse Event (SAE).	Any adverse event that: 
  results in death,  is life-threatening*,  requires hospitalisation or prolongation of existing hospitalisation**,  results in persistent or significant disability or incapacity, or  consists of a congenital anomaly or birth defect

*A life-threatening event, this refers to an event in which the participant was at risk of death at the time of the event; it does not refer to an event which hypothetically might have caused death if it were more severe.

** Hospitalisation is defined as an in-patient admission, regardless of length of stay. Hospitalisation for pre-existing Conditions or planned upcoming surgeries (ie. Other knee replaced), including elective procedures do not constitute an SAE.

Table 3. Definition of adverse events

Category	Definition
Non-severe	The adverse event does not interfere with the participant's daily routine, and does not require further procedure; it causes slight discomfort
Life threatening	The adverse event interferes with some aspects of the participant's routine, or requires further procedure, but is not damaging to health; it causes moderate discomfort
Hospitalisation required / prolonged	The adverse event results in alteration, discomfort or disability which is clearly damaging to health
Permanent of significant disability/ incapacity	Permanent of significant disability/ incapacity

Table 4. Severity of SAE classification

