14.0 Recording of Serious Adverse Events

All serious adverse events will be recorded in the medical records and the CRF, and the sites AE log.

All serious adverse events (SAEs) must be recorded on a serious adverse event form (appendix 19.4). The Principal Investigator will complete the SAE form and the form will be emailed to the SJOG HREC Committee within 5 working days of becoming aware of the event. The Chief Investigator will respond to any SAE queries raised by the primary HREC as soon as possible. Where the event is unexpected and thought to be related to the procedure this must be reported by the Investigator to the Therapeutic Goods Administration via the Incident Reporting and Investigation Scheme within 15 days.

All SAE's will be reported as per the flow diagram below.

[figure not shown]

Diagram 1. Flow chart for reporting SAE's.

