Appendix 19.4 Local Site SAE / AE Form

Local Site SAE/SUSAR/USADE Report

This is a dynamic PDF form. Depending on your answers, certain questions will appear and text boxes will expand.

Full Study Title:

Short Title/Acronym: SJGHC HREC Ref:

Event Type: Study Type: SJGHC Participating Site:

Event Term:

Investigator(s): Report # to SJGHC HREC:

Date of Event: Study ID: Age: Female Male

Event Description and Management:

Event Outcome:

- Fatal
- Life Threatening
- Hospitalisation required/prolonged
- Permanent or significant disability/incapacity
- Other:

Event Relationship to Study

- Related to
- Probably related
- Possibly related
- Not related

Is this event a documented side effect? (i.e. specified in the study protocol)

Yes No

How often has this same event occurred to date in the present study?

Yes No

As a researcher conducting this clinical trial, in your opinion, are any amendments required to the Protocol and/or Participant Information and Consent Form(s)?

Yes No

As a researcher conducting this clinical trial, in your opinion, are there any implications for the continued conduct of the study?

Yes No

Name:

Position:

Signature:

(click box to insert image of signature)

Date:

Please ensure any person who has electronically signed this document is copied in on the submission to the Ethics Office.

Please attach any supporting documentation to this form, including reports from the IDMC when they are received.

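### Table 4 attaches severity definitions to seriousness labels and so contradicts Table 3 on life-threatening events and hospitalisation; SAE categories could be recorded inconsistently

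*Combined protocol and SAP*

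**What the plan says.** **Table 3 (section 12.1)** lists what makes an adverse event serious: death, threat to life, hospitalisation or its prolongation, lasting disability, or congenital anomaly. Two footnotes fix the terms. On life-threatening: "this refers to an event in which the participant was at risk of death at the time of the event". On admission: "Hospitalisation is defined as an in-patient admission, regardless of length of stay".

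**Table 4 (same section)** is captioned "Table 4. Severity of SAE classification". It has four categories. *Non-severe* means slight discomfort with no effect on daily routine and no further procedure. *Life threatening* means some interference with routine or a further procedure, with the qualifier "but is not damaging to health; it causes moderate discomfort". *Hospitalisation required / prolonged* is defined as "The adverse event results in alteration, discomfort or disability which is clearly damaging to health". The fourth category, permanent or significant disability, has a definition that repeats its label.

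**Where these are used.** Under Recording of Serious Adverse Events (section 14.0), every SAE goes on the Appendix 19.4 form, and "the form will be emailed to the SJOG HREC Committee within 5 working days of becoming aware of the event". That form has an *Event Outcome* field with five options: fatal, life threatening, "Hospitalisation required/prolonged", permanent or significant disability or incapacity, and other. It defines none of them. Section 14.2 separately requires the severity of each SAE to be documented in the research record.

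**The concern.** Seriousness and severity are different attributes. Seriousness is a regulatory classification by outcome or by threat to life. Severity is a grade of intensity. Table 4 takes its labels from the first and its definitions from the second, so a reader who applies it literally assigns a seriousness label by a severity rule.

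The error runs in both directions. A moderate event picks up the label *Life threatening*. An event that does put the patient at risk of death has no Table 4 definition that describes it.

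What is at stake is whether the safety record can be interpreted. Section 1.2 says that there are no long-term longevity data for functional alignment and that its risks and benefits still have to be defined. A count of life-threatening events is of little use if some staff worked from Table 3 and others from Table 4.

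**Working it through.** No arithmetic in the plan bears on this. The check sets the definitions side by side and asks whether any reading reconciles them.

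**Step 1. Compare the rows.**

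| Label in Table 4 | Definition in Table 4 | Meaning in Table 3 | Agreement |
|---|---|---|---|
| Non-severe | Slight discomfort, no procedure | Not a Table 3 term | No conflict |
| Life threatening | Some interference with routine, "or requires further procedure, but is not damaging to health; it causes moderate discomfort" | Actual risk of death when it happened | Contradicts |
| Hospitalisation required / prolonged | Clear damage to health; admission not mentioned | Any in-patient admission | Contradicts |
| Permanent or significant disability | Repeats the label | Persistent or significant disability | No conflict |

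Two of the four rows conflict.

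**Step 2. Could the rows have slipped in the PDF text?** Four labels and four definitions can be paired in 4 × 3 × 2 × 1 = 24 ways. None of the four definitions mentions risk of death, so none of the 24 pairings gives *Life threatening* its Table 3 meaning. None mentions admission either, so the same holds for *Hospitalisation*. Slipped rows do not explain the mismatch.

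**Step 3. Apply both tables to the same events.**

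- *Unplanned admission for a further procedure, with no damage to health.* Table 3: an SAE, by hospitalisation. Table 4: the definition that fits is the one against *Life threatening*.
- *Event with actual risk of death that damages health but leaves no lasting disability.* Table 3: an SAE, life-threatening. Table 4: the definition that fits is the one against *Hospitalisation required / prolonged*.
- *Brief unplanned admission, slight discomfort, no procedure.* Table 3: an SAE, by hospitalisation. Table 4: *Non-severe*.

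In the first two cases the two tables return different seriousness labels for one event. The third is coherent only if Table 4 is read as a pure severity scale, and its middle two labels prevent that reading.

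**Step 4. Trace where a wrong label could go.**

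- SAE status comes from Table 3. The 5-working-day report depends on SAE status, and the 15-day report to the regulator on the event being unexpected and related. Neither depends on Table 4.
- The severity entry required by section 14.2 has only Table 4 to draw on, because it is the only severity scale in the document.
- On the Appendix 19.4 form, three of the five outcome options nearly match Table 4 labels and none is defined. Staff have to look to section 12.1, where they find both meanings.

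**The case against.** The best defence is that little depends on Table 4. The Table 3 footnote is explicit and stands in the same section, so the protocol does have a valid definition of life-threatening, and staff who follow it will classify correctly. The Appendix 19.4 form has no severity field and does not cite Table 4. The fault applies to both arms alike and does not touch the Forgotten Joint Score analysis or the sample size. All of this stands, and it limits the point to inconsistent recording where Table 4 is applied.

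A second defence is lost text. The contents list a section 12.2 on outcomes that does not appear in the text available, and a sentence after Table 5 starts part-way through. Severity and outcome material may have been separated in the source. This cannot be excluded, but missing text would not undo the pairing that is printed.

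A reader might also infer more than the documents support:

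- *That SAEs would be missed or reported late.* No: Table 3 governs both.
- *That reports to the ethics committee will be wrong.* They could be, where staff take the meaning of a label from Table 4. The documents do not direct them to do so.
- *That severity tables by arm would be distorted.* No such table is planned. Section 6.2.2 says only in general terms that summaries are given per treatment group.
- *That Appendix 19.4 gives a conflicting meaning.* It defines no terms. The conflict is between Tables 3 and 4.
- *That deaths would go unrecorded because Table 4 has no fatal row.* Death is in Table 3, on the Appendix 19.4 form and on the End of Study form (Appendix 19.2).

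**Conclusion.** The contradiction is real. Two of the four rows of Table 4 conflict with the Table 3 footnotes, and no re-pairing of rows removes the conflict. Applied as written, Table 4 classes an SAE that needs a further procedure without damage to health as life threatening, and gives no fitting definition for an event that truly is.

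The consequence is limited to the category assigned to an SAE: the severity entry under section 14.2 and, where staff rely on Table 4, the outcome box on the Appendix 19.4 form. Safety records could therefore be inconsistent. The documents give no expected event rate, so the number of affected records cannot be stated.

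This rests on two assumptions: that Table 4 as extracted matches the source, and that at least some staff would use it, which is reasonable given that it is the only severity scale provided. It is worth correcting because a stated rule gives a wrong classification and the correction is small.

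**What to change.** Reconcile Table 4 with Table 3 and Appendix 19.4:

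1. Keep the seriousness labels (life-threatening, hospitalisation, disability) with their Table 3 meanings only.
2. Attach Table 4's existing definitions to a separate severity grade with severity words as labels, so that each SAE carries both a seriousness criterion and a severity grade.
3. Align the protocol's outcome list with the Appendix 19.4 options, including fatal, and state that the form's terms carry their Table 3 meanings.
4. Re-check any events already graded under the current Table 4.

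The cost is one table edit and the re-check. No treatment, visit, sample size or reporting deadline changes.

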13.3 Causality

Category	Definition
Related	There is clear evidence to suggest a causal relationship, and other possible contributing factors can be ruled out.
Probably related	There is evidence to suggest a causal relationship, and the influence of other factors is unlikely
Possibly related	There is some evidence to suggest a causal relationship (e.g. the event occurred within a reasonable time after administration of the study procedure). However, the influence of other factors may have contributed to the event (e.g. the participant's clinical condition, other concomitant events).
Not related	There is no evidence of any causal relationship.
Not assessable	Unable to assess on information available

Table 5. Causality of SAE classification

capture events related to the mFA TKA and kFA TKA. The assessment of relationship of an adverse event to these additional safety issue(s) will also be carried out as part of the study.

14.0 Recording of Serious Adverse Events

All serious adverse events will be recorded in the medical records and the CRF, and the sites AE log.

All serious adverse events (SAEs) must be recorded on a serious adverse event form (appendix 19.4). The Principal Investigator will complete the SAE form and the form will be emailed to the SJOG HREC Committee within 5 working days of becoming aware of the event. The Chief Investigator will respond to any SAE queries raised by the primary HREC as soon as possible. Where the event is unexpected and thought to be related to the procedure this must be reported by the Investigator to the Therapeutic Goods Administration via the Incident Reporting and Investigation Scheme within 15 days.

All SAE's will be reported as per the flow diagram below.

[figure not shown]

Diagram 1. Flow chart for reporting SAE's.

14.0 Reporting Incidents

14.1 Protocol deviations and notification of protocol violations

A deviation is usually an unintended departure from the expected conduct of the study protocol, which does not need to be reported to the TGA. The principal investigator will monitor protocol deviations.

A protocol violation is a breach which is likely to effect to a significant degree –

- the safety or physical or mental integrity of the participants of the study; or
- the scientific value of the study.

The Chief investigator and IDSM will be notified immediately of any case where the above definition applies during the study conduct phase.

14.2 Reporting Incidents involving a medical device

Adverse device effects (complications) are defined as any of the following:

- a) Any device component failure (e.g. excessive migration of the implant or failure otherwise).
- b) Local complications arising from use of the TKA implants to include osteolysis, inflammation, local tissue reaction, periprosthetic fracture.
- c) Bone fracture during implantation
- d) Nerve damage arising from implant placement (as evidenced immediate postoperative by motor and/or sensory deficit not present preoperatively).
- e) Large vessel damage arising during surgery (with large blood loss, i.e. > 1500 ml).
- f) Prosthetic joint infection
- g) Surgical site infection
- h) Loosening of prosthetic components
- i) Other adverse events that are deemed device related and serious.

All serious adverse events, life-threatening problems, or deaths that occur during or following the use of the devices during the study should be fully documented in the research record by the Chief Investigator including the onset date, complete description of the event, severity, duration, action taken, and outcome. The event should be documented at the appropriate interval case report form. The Chief Investigator will be responsible for notifying the reviewing Research Ethics Committee, of any unanticipated adverse events according to local regulations.

The Chief Investigator will record all non-serious adverse events on the appropriate case report form.

Some adverse events may lead to subsequent surgical intervention. The surgical intervention should be reported separately from the presentation of the other adverse event. For example, if the adverse event is reported at the 3 months visit and a revision subsequently occurs after the 3 months visit, the revision should be reported in the next follow-up visit.

In the short term, revisions will usually occur due to acute/chronic infection, instability, and/or subject experiencing severe pain due to various causes. This data will be used in combination with clinical assessment, target history / examination and further investigation to determine likelihood of requiring revision.

For all cases where revision was necessary, the investigator must record and forward a description of intraoperative findings including: presence of local reaction to implant, gross subsidence of implant, and any intraoperative findings relating to the device failure. This information will be recorded by the intra-operative

product specialist, and information will be submitted to the TGA via the medical device incident reporting guide. Explant analysis will occur throughout the duration of this study.

15.0 Training

The Chief Investigator will review and provide assurances of the training and experience of all staff working on this study. Appropriate training records will be maintained in the study files. All personnel working on this study will have completed the Guideline for Good Clinical Practice ICH E6(R2) Qualification.

